## **Background**

Neuropathy means the damage of peripheral nerves due to various conditions like chronic diseases, injury or as a side effect of specific medications. In particular, chemotherapy-induced peripheral neuropathy (CIPN), a side effect of antineoplastic medication, was reported to occur in about 68% of the patients receiving chemotherapy (Seretny et al., 2014). CIPN does not only limit quality of life due to neuropathic symptoms but also may lead to dose reductions or premature interruption of therapy and thus to suboptimal cancer treatment.

Patients with neuropathy suffer from sensory disturbances as tingling, numbness, burning pain or sleep disturbances and even though numerous drugs are available, it is still difficult to sufficiently control these symptoms (Javed et al., 2018).

High tone therapy / high tone external muscle stimulation (HTEMS) seems to be an effective treatment for neuropathic symptoms. Previous studies observed promising results in diabetics (Hidmark et al., 2017; Humpert et al., 2009; Kempf & Martin, 2010; Reichstein et al., 2005) and chronic kidney disease (CKD) patients (Klassen et al., 2012; Strempska et al., 2013).

To date, there is no investigation on HTEMS in patients with chemotherapy induced neuropathy.

Therefore, this aim of this project is to test if HTEMS would bring about a stronger decrease in neuropathic symptoms in this specific patient group, compared to a placebo treatment.

The primary objective is the alleviation of paresthesias. The secondary objective focuses on detailed symptoms of neuropathy as well as on health-related quality of life.

## **Methods**

### **Design**

This two-center study will be conducted at the Departments of Physical and Rehabilitation Medicine of the Danube Hospital and the Wilhelminen Hospital, Vienna, Austria. This study will be randomized, double-blind and placebo-controlled.

### **Subjects**

Female and male patients of the oncologic clinics of the Danube Hospital and Wilhelminen Hospital will be screened for eligibility and invited to participate in the study. The inclusion- and exclusion criteria will be checked at the Departments of Physical and Rehabilitation Medicine. Before any study-related procedure, written informed consent will be obtained and subjects will be randomized consecutively. The allocation to group A or B will be performed according to a randomization protocol designed by the Directorate General, Board Division of Health Care Management. This protocol will be based on online randomization.

Inclusion criteria will be:

- Patients with histologically verified colorectal cancer and adjuvant treatment with a platinum derivative (e.g., cisplatin, oxaliplatin): This group was chosen due to relatively high risk of neuropathy due to this special therapeutic agent (Park et al., 2013; Seretny et al., 2014).
- Cumulative dose of at least 3 cycles
- Interval of 2 weeks since the last chemotherapeutic cycle in order to prevent false worsenings due to delayed neurotoxic effects
- Life expectancy of at least 3 months
- Stable medication (no changes of especially pain medication during the study)
- Eastern Cooperative Oncology Group (ECOG) Performance Status score of 0-2 (that is, the capability to walk and to spend less than 50% of waking hours sitting or lying)
- Ability to walk (with or without aids)
- European Organisation for Research and Treatment of Cancer (EORTC) common toxicity criteria (CTC) peripheral sensory neuropathy grade 1 or 2
- Intensity of paresthesias of 3/10 or higher on the Numeric Rating Scale (NRS)

Exclusion criteria will be:

- Prevalent neuropathy of different etiology
- Serious central-neurological or psychiatric disorder that would interfere with a proper order of the study, according to the judgement of the investigators
- Epilepsy
- Minors or persons unable to give informed consent
- Current neurotoxic medication
- Implanted pacemakers or defibrillators
- Pregnancy
- Wounds in the area to be treated, acute local or systemic infection
- Peripheral arterial occlusive disease > grade 2

## **Treatment**

The HiTop® 191 (GBO Medizintechnik AG, Rimbach, Germany) is a CE-certified and patented (European Patent 1322379B1) medical product.

It delivers medium frequency alternating current and to date, no undesirable side effects have been reported. In detail, the carrier frequency lies between 4-33kHz and is modulated at a defined frequency of 20Hz. This procedure is called SimulFAM® (simultaneous frequency amplitude modulation).

The electrodes will be placed onto the calfs and soles, respectively.

The HiTop treatment does not involve a typical “electricity sensation” but rather only a feeling of muscular contraction in some but not all persons. In other words, according to personal communications with several rehabilitation units, some persons are do not feel anything during the *verum* treatment. Therefore, a placebo-controlled study seems to be feasible.

The mechanisms of action have not been clarified yet. However, two major possible ways have been discussed: 1. spinal stimulation, thereby decreasing the excitability of small fibers (Humpert et al., 2009) and 2. promotion of attachment and differentiation of hematopoietic stem cells (Hidmark et al., 2017). Concerning stem cells, there is only a single study on diabetics reporting a higher number of molecules mediating attachment and differentiation of hematopoietic stem cells. However, in this study there was no

control group. Therefore, the possible effect via stem cells should be called a hypothesis rather than a verified mechanism.

Nevertheless, due to accumulation of platin in the dorsal root ganglia chemotherapy-induced neuropathy seems to result from ganglionopathy with subsequent axonal hyperexcitability (Beijers et al., 2014). Therefore, we rather think that the effect of high tone therapy seems to result from sensory afferent actions.

In the placebo group, a placebo device of the same design will be used with no current output.

To ensure a double-blind procedure, the participants will be supervised by two physicians per center. Physician one will perform the assessments and physician two will manage the randomization and instruction in the handling of the device. All subjects will be informed that they may feel tingling or muscle contraction during the treatment but also about the possibility of not feeling any sensations. Subjects will be required not to tell physician one if they felt tingling or contractions.

Previous studies observed alleviation of neuropathic symptoms after a relatively short treatment period (Hidmark et al., 2017; Humpert et al., 2009; Kempf & Martin, 2010; Reichstein et al., 2005). However, most of these studies had no control group and therefore, the data on the effect of high tone therapy is weak.

Therefore, the treatment phase in our study will last three weeks. One treatment session will take about 60min. The minimum number of treatment sessions to be completed will be 5 out of 7 days. The device saves minutes of treatment and therefore offers the clinician to monitor the participants' compliance. Therefore, the treatment will be home-based.

## **Assessments**

Assessments will be carried out at the following points of time: Baseline, after the first treatment week, at the end of the treatment phase and follow up after two weeks.

After completing the follow-up assessment, the participants will be unblinded and subjects of the placebo group will be offered to join the treatment group (opt in).

The baseline assessment includes a test of vibration sensation by using a clanging tuning fork (Panosyan et al., 2016). In this examination, certain anatomical localizations will be touched with the tuning fork (i.e., the dorsum of the interphalangeal joint of the hallux and the medial malleolus). Several studies reported that this test not only detects peripheral neuropathy accurately but also that it is superior to the monofilament test (Meijer et al., 2005; Oyer et al., 2007). Moreover, normative values for several age groups have been published (Martina et al., 1998).

In addition, full medical and social history will be collected, including:

- demographic data (date of birth, height, weight)
- previous conditions and operations
- course and treatment of the current cancer, duration of neuropathy
- (pain) medication (patients will be required not to change their medication during the study)
- Walking aids
- Need for social / nurse support (type of support and hours per week)
- Social history (profession, level of education, family status)

The following outcome parameters will be determined and quantified as part of all assessments:

### **Pain and sensory disturbances**

- Numeric rating scale (NRS, 0-10): Paresthesia intensity, mental stress due to paraesthesia, pain intensity, mental stress due to pain, tightness/pressure intensity and mental stress due to tightness/pressure
- European Organisation for Research and Treatment of Cancer Chemotherapy-Induced Peripheral Neuropathy 20 questionnaire (EORTC CIPN 20): This is an international questionnaire to assess chemotherapy induced neuropathy with a

sensory scale, motor scale as well as an autonomic scale (Postma et al., 2005). The CIPN 20 questionnaire has been used in recent studies (Coyne et al., 2013; Gewandter et al., 2018).

- Neuropathy Symptom Score (NSS): This validated questionnaire assesses and quantifies neuropathic symptoms and has been used in recent studies (Hidmark et al., 2017; Jende et al., 2018; Mao et al., 2018).

### **Quality of life**

- EORTC Core 30 (EORTC C30) questionnaire: This questionnaire is designed to assess health-related quality of life specifically in cancer patients and has been used recently (Elfeki et al., 2018).

## **Objectives**

The primary objective is to compare the changes in intensity of paresthesias between the two patient groups. This will be performed via standardized questionnaires with numeric rating scales (NRS) in the baseline assessment, after the first treatment week, at the end of the treatment phase and follow up after two weeks.

The secondary objective is to evaluate neuropathic symptoms further in detail and to assess quality of life via standardized questionnaires with NRS as well as via internationally accepted questionnaires.

## **Hypothesis**

We hypothesize that high tone therapy will bring about a significantly stronger reduction in neuropathic symptoms, compared to the placebo treatment.

## **Statistical analysis**

To show that the primary objective, changes in intensity of paresthesias measured with the numeric rating scale, will bring about a significantly stronger reduction in the intervention group, a repeated measures analysis of variance will be conducted. A mean value out of 8 questions will be calculated which will be compared between the intervention group and the placebo group (between-subject-factor) and between 4 measurements (within-subject-factor). A 4\*2 within-between-interaction can point out differences in intensity of paresthesias between all times of measurements and between both groups. In a two-sided test the alpha level will be set at 0.05 to show significant effects.

Also, the secondary objectives, measured with standardized questionnaires, will be analysed in a repeated measures analysis of variance model, since all questionnaires will be tested at 4 times of measurement. With the EORTC QLQ-C30 (3rd version) a global health status, functional scales and symptom scales are calculated. With the EORTC QLQ-CIPN20 moreover a sensory scale, a motor scale and an autonomic scale are calculated. Since all subscales of both questionnaires are metric, a multivariate model can be calculated via repeated measures analysis of variance (alpha 0.05, two-sided)

In addition, a neuropathic-symptom-score (NSS) with 5 more questions is calculated. At a range of 0-10 points patients can be classified in 4 groups (<3 points, 3-5 points, 6-8 points, 9-10 points) and a Chi-square analysis can show differences in frequencies

at 4 times of measurement (alpha 0.05). Under the assumption of a normal distribution of the residuals and homoscedasticity the 4 classified groups of the NSS questionnaire could be used to build an additional factor and show differences in a repeated measures ANOVA between the 4 groups (additional between-subject-factor) in the primary objective and the secondary objective model (alpha 0.05, two-sided)

Logistic-Regression models could show combined effects of primary and secondary objectives, if the quality of data is sufficient (alpha 0.05). If the quality of data is insufficient simple effects between primary and secondary objectives, and all subscales of the secondary objectives questionnaires, could be shown with Pearson correlations (alpha 0.05, two-sided).

Descriptive statistics and frequencies will be calculated for sampling variables.

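### Optional improvement: the repeated measures ANOVA named for the primary test normally keeps only patients with all four assessments, whereas a mixed model would test the same interaction and keep partial records

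*Protocol*

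**What the plan says.** The Statistical analysis section of the protocol commits the primary objective to one model: "a repeated measures analysis of variance will be conducted". Group is the between-subject factor and the four measurement times are the within-subject factor. The result is read from the interaction: the "within-between-interaction can point out differences in intensity of paresthesias between all times of measurements and between both groups". On the error rate it says: "In a two-sided test the alpha level will be set at 0.05 to show significant effects".

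The Assessments section places the four measurements at "Baseline, after the first treatment week, at the end of the treatment phase and follow up after two weeks". The Treatment section adds that "the treatment phase in our study will last three weeks", so the last value falls about five weeks after baseline (3 + 2).

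One sentence in Assessments bears on attendance: "After completing the follow-up assessment, the participants will be unblinded and subjects of the placebo group will be offered to join the treatment group".

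A later sentence in Statistical analysis allows the four NSS classes to enter the primary and secondary ANOVA models as a further between-subject factor. The protocol does not mention complete cases, imputation or a mixed model. The SAP was not available for this review.

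**The concern.** A classical repeated measures ANOVA needs a value at every level of the within-subject factor. Standard software therefore drops a patient with one missing assessment from the whole interaction test, whichever assessment it is. The least welcome case here is a patient who is fully observed through the end of treatment and misses only the later follow-up: the end-of-treatment score exists but contributes nothing to the primary test.

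What is at stake is power for the primary comparison, and only if visits are missed. A likelihood-based mixed model tests the same interaction from all observed values.

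**Working it through.** **Inputs.** From the protocol: two groups, four visits at about weeks 0, 1, 3 and 5, a 3-df interaction, two-sided alpha 0.05. The protocol has no power calculation to reproduce. Assumed for illustration: group differences of 0, 0.3, 0.6, 0.6 SD at the four visits; 30 or 50 patients per arm; within-patient correlation either constant at 0.5 or 0.8 per week, decaying with time apart; baseline always observed; missingness completely at random and equal in both arms.

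**Step 1: same hypothesis.** In one simulated complete data set with 30 per arm, the ANOVA interaction gives F = 4.466 on 3 and 3 × (60 − 2) = 174 df, p = 0.0048. A random-intercept mixed model gives Wald/3 = 4.466. The question asked is the same. The model proposed below has an unstructured covariance, which costs some power on complete data (step 4).

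**Step 2: patients dropped.** Let p be the chance of missing a visit.
- Only the follow-up can be missed: p, so 5% or 10%.
- Dropout at each post-baseline visit (monotone), or independent misses: 1 − (1 − p)³ = 0.143 for p = 0.05 and 0.271 for p = 0.10.

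Dropped although the week-3 value was observed, as a share of all patients:
- follow-up only: p = 0.05 or 0.10
- monotone: (1 − p)² × p = 0.045 or 0.081
- independent: (1 − p) − (1 − p)³ = 0.093 or 0.171

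**Step 3: precision of the change from baseline to week 3.** With Σ the within-patient covariance, c the contrast and w the share of complete records, the large-sample variance per patient is c′Σc / w from complete records. From all data it is c′I⁻¹c, where I sums the information from each missingness pattern. When only the follow-up is missed, the ratio of the two is exactly 1/(1 − p).

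| Pattern | p = 0.05 | p = 0.10 |
|---|---|---|
| Follow-up only | 1.053 | 1.111 |
| Monotone | 1.084-1.087 | 1.177-1.184 |
| Independent | 1.129-1.140 | 1.282-1.306 |

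Ranges run from constant to decaying correlation. A separate recalculation reproduces these ratios and the shares in step 2.

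**Step 4: power of the interaction test.** The comparison is a Greenhouse-Geisser-corrected ANOVA on complete records against an unstructured mixed model with a small-sample F, 5,000 simulated trials per setting. Two of the four settings are shown: ANOVA / mixed, in per cent, with the difference in points.

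| Pattern | Incomplete | Constant 0.5, 50 per arm | Decaying 0.8, 30 per arm |
|---|---|---|---|
| No misses | 0% | 84.4 / 83.9 (−0.5) | 52.8 / 50.0 (−2.8) |
| Follow-up only, 5% | 5% | 82.0 / 83.0 (+1.0) | 51.6 / 51.3 (−0.3) |
| Follow-up only, 10% | 10% | 79.8 / 82.7 (+2.9) | 49.1 / 51.0 (+1.9) |
| Monotone, 5% per visit | 14.3% | 76.4 / 79.1 (+2.7) | 46.7 / 48.3 (+1.6) |
| Monotone, 10% per visit | 27.1% | 69.2 / 74.9 (+5.7) | 39.9 / 45.1 (+5.2) |
| Independent, 5% per visit | 14.3% | 77.2 / 82.3 (+5.1) | 47.1 / 49.3 (+2.2) |
| Independent, 10% per visit | 27.1% | 69.2 / 80.6 (+11.4) | 38.7 / 47.8 (+9.1) |

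Type I error over all settings was 0.043-0.058 for the ANOVA and 0.045-0.057 for the mixed model.

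**Step 5: how far to trust the decimals.** One simulated power near 50% has a standard error of √(0.5 × 0.5 / 5000) = 0.7 points; the paired differences have 0.3-0.7. Some entries are visibly noise. Mixed-model power cannot truly rise from 50.0 to 51.3 when follow-up data are removed, and the +2.2 in the last column is nearer +3.4 by an expected-information calculation. Linear interpolation puts break-even at 5 × 0.5/1.5 = 1.7% of patients incomplete in one column and 5 + 5 × 0.3/2.2 = 5.7% in the other. Across settings, and given the noise, roughly 3-7% is a fair summary. Only rounded ranges are carried forward.

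**The case against.** The strongest reply is that nothing in the protocol is wrong. Repeated measures ANOVA is a conventional and valid test. The protocol nowhere orders deletion of incomplete patients, and how missed visits are handled is commonly left to the SAP, which could keep the ANOVA and add imputation without contradicting the protocol. The schedule is short and treatment is home-based. Unblinding and the placebo group's offer of active treatment come only after the follow-up assessment, which gives patients a reason to attend. In the case that motivates the point, 5% missing only the follow-up, the difference is between slightly negative and about +1 point. The largest gains need about 27% of records incomplete through scattered misses, which nothing in the document suggests.

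Most of this stands. It limits the point to an optional one and rules out quoting the upper figures as an expectation. It does not remove the point, because the protocol itself names the model, and that model as normally fitted discards partial records.

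The objection also shows that changing the primary sentence alone would leave the NSS-group sentence extending a primary ANOVA that no longer exists. That is accepted and included in the fix.

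**Conclusion.** The point holds as a cheap improvement to consider. Under the stated assumptions the mixed model loses about 0 to 3 power points if every visit is attended and breaks even at roughly 3-7% of patients incomplete. It gains about 1-3 points if 10% miss only the follow-up, and about 2-12 points if 14-27% of records are incomplete. Every figure rests on assumed effects, sample size, correlation and missingness, because the protocol gives none of them.

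A reader might infer three stronger things that the document does not support:
- **That the planned ANOVA is invalid or biased.** Its type I error was sound in the check, and nothing in the document shows that missingness would relate to outcome.
- **That the plan neglects missing data.** The SAP was not seen and may set a rule.
- **That the mixed model is always more powerful.** With complete data it is slightly weaker than the corrected ANOVA.

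**What to change.** In the Statistical analysis section, replace the primary model sentence with wording such as:

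*The group-by-visit interaction will be tested with a likelihood-based mixed model for repeated measures (group, categorical visit, group-by-visit interaction, unstructured covariance, small-sample degrees of freedom), using every available assessment.*

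Reword the later sentence on adding NSS classes as a factor so that it extends this model where it refers to the primary objective. The optional multivariate EORTC model can stay as it is. If a SAP exists, the two documents should name the same model.

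The cost is two edits to the text and standard software, with no extra data or visits. There are two downsides. The model relies on data being missing at random, although complete-record analysis usually needs the stricter condition of missing completely at random. It also gives up the small amount of power stated above if no visit is missed.

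### The primary test averages 8 unidentified questions that do not match the six listed NRS ratings, so a mixed-symptom mean could be read as paresthesia intensity

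*Protocol*

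**What the plan says.** Background states the aim: "The primary objective is the alleviation of paresthesias". Objectives repeats it as a comparison: "The primary objective is to compare the changes in intensity of paresthesias between the two patient groups". It adds that measurement will be by questionnaires using numeric rating scales. Other symptoms go elsewhere: "The secondary objective is to evaluate neuropathic symptoms further in detail".

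The Assessments section introduces what is collected at every visit: "The following outcome parameters will be determined and quantified as part of all assessments". Under Pain and sensory disturbances, the 0-10 NRS entry reads: "Paresthesia intensity, mental stress due to paraesthesia, pain intensity, mental stress due to pain, tightness/pressure intensity and mental stress due to tightness/pressure".

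Statistical analysis first names paresthesia intensity on the NRS as the primary objective. It then specifies the variable: "A mean value out of 8 questions will be calculated which will be compared between the intervention group and the placebo group". The group-by-time interaction on that variable, it says, "can point out differences in intensity of paresthesias between all times of measurements and between both groups".

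**The concern.** The protocol fixes the primary variable by item count and summary (a mean of eight), but no section says which eight questions are averaged. The outcome list does not yield eight NRS questions. With one question per listed rating, any mean of two or more must include a mental-stress, pain or tightness/pressure rating. Two competent analysts could therefore build different primary variables from the same text.

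What is at stake is what the primary result means. If the mean covers several symptoms, a group difference could come from pain or mental stress and still be reported as paresthesia relief. Conversely, a real effect confined to paresthesia could be diluted by items that do not move. Dilution is plausible because the inclusion criteria require paresthesia of at least 3 out of 10 but set no minimum for pain or tightness, so some participants may enter with little of either to improve.

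**Working it through.** The protocol gives no sample size, SD or inter-item correlation, so there is no power figure to reproduce. The check is a count, followed by a comparison of sections.

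**Inputs**

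- Questions in the primary mean (Statistical analysis): 8.
- NRS ratings (Pain and sensory disturbances): 3 symptoms × 2 ratings each (intensity, mental stress) = 6.
- Of these, paresthesia intensity: 1. Others: 6 − 1 = 5.
- NSS questions (Statistical analysis): 5, described as additional.
- CIPN20: 20 questions, going by its name, scored as sensory, motor and autonomic scales.

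**Can the list produce 8?**

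- Paresthesia intensity only: 1.
- Both paresthesia ratings: 2.
- The three intensity ratings, or the three mental-stress ratings: 3.
- All NRS ratings: 6. This leaves 8 − 6 = 2 questions unaccounted for.
- NSS alone: 5. CIPN20 alone: 20.
- Three NRS ratings plus the NSS: 3 + 5 = 8. The total fits, but Statistical analysis introduces the NSS questions as further ones and gives them their own 0-10 score, so they are not part of the eight.
- Six NRS ratings plus CIPN20 plus NSS: 6 + 1 + 1 = 8 entries. These are list entries, not questions, and the two questionnaires are analysed separately as secondary.

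No set that is consistent with the rest of Statistical analysis gives eight questions.

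**Which content do the sections point to?**

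- Towards paresthesia only: Background and Objectives name paresthesia as primary, Objectives places other neuropathic symptoms under the secondary objective, and Statistical analysis refers to paresthesia intensity immediately before and after the eight-question sentence.
- Towards a mixed mean: the only NRS list has five non-paresthesia-intensity ratings out of six, and the Hypothesis section is worded for neuropathic symptoms in general.
- Neutral: Objectives mentions NRS-based questionnaires for the primary objective, which fits a multi-item paresthesia instrument. It uses similar wording for the secondary objective, so the phrase does not single out paresthesia items.

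The intended content is probably paresthesia only, but the text does not settle it.

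**The case against.** The strongest reply is that six ratings and eight questions are different units. The outcome list says what is rated, not how many questions are asked. Paresthesia intensity could be asked in several questions, for example by body site, and the Objectives wording about NRS questionnaires fits that. On this reading Background, Objectives and Statistical analysis agree, the outcome list is merely terse, and there is no bias. Item wording is also commonly left to the case report form or to an SAP, which is not at hand.

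Much of this stands. It means the harm is conditional, and an omitted item list would not by itself be a finding. It does not remove the mismatch. The protocol did not leave the primary variable open: it fixed it as a mean of eight, beside an outcome list with one paresthesia-intensity rating, and names no eight-item paresthesia questionnaire. An SAP could add scoring detail, but the protocol's sections would still need to be brought into line.

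A reader might go further and infer that the primary variable does mix symptoms, so that the primary test certainly misses its objective. The documents do not support that, because an all-paresthesia set of eight remains possible. A reader might also infer from "After completing the follow-up assessment, the participants will be unblinded" that the items could be chosen once results are known. That sentence concerns participants individually. It does not say that anyone sees outcomes by group, and the item list may already exist.

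**Conclusion.** The point holds as a mismatch within the protocol about its primary variable: eight questions averaged, six NRS ratings listed, one of them paresthesia intensity, and no section identifying the eight. Confidence in this is high, since it rests only on counts and wording in the document.

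The consequence is conditional. Misattributed or diluted effects arise only if the mean includes ratings other than paresthesia intensity, which the text allows but does not state. Confidence in the harm is therefore moderate. The protocol gives nothing from which to compute its size or direction, and any figure would rest on assumed item content, correlations and responses. This should be fixed, but it is not evidence that the primary analysis is invalid.

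**What to change.** Before any analysis of outcomes by group, reconcile Pain and sensory disturbances, Objectives and Statistical analysis so that the primary variable contains only NRS paresthesia-intensity items:

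- List those items and their scoring in the outcome section, and average only them, however many there are.
- If there is only one, use the single NRS paresthesia-intensity rating already listed.
- Analyse any pain, tightness/pressure or mental-stress item as secondary, under the repeated measures model the protocol already states.

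The cost is a protocol amendment. No new data are needed, provided the ratings are collected as listed. If all eight questions already rate paresthesia intensity, the analysis does not change and the amendment only names them. If fewer do, the primary variable changes and may be noisier than an eight-item mean. The effect on power cannot be judged from the protocol, which gives no sample size or SD.

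### The primary repeated measures ANOVA treats the pre-treatment baseline as one of four outcome levels: it tests the stated objective without bias, but less precisely than adjusting for that baseline

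*Protocol*

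**What the plan says.** The Assessments section sets four "points of time: Baseline, after the first treatment week, at the end of the treatment phase and follow up after two weeks". The Objectives section states "The primary objective is to compare the changes in intensity of paresthesias between the two patient groups", measured "in the baseline assessment, after the first treatment week, at the end of the treatment phase and follow up after two weeks".

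The Statistical analysis section names a repeated measures ANOVA with group as the between-subject factor. It compares the score between the groups "and between 4 measurements (within-subject-factor". The primary test is the 4 by 2 interaction at two-sided 0.05: the "within-between-interaction can point out differences in intensity of paresthesias between all times of measurements and between both groups". No baseline covariate is named.

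The secondary questionnaires "will be analysed in a repeated measures analysis of variance model, since all questionnaires will be tested at 4 times of measurement". For the EORTC subscales the wording is looser: "a multivariate model can be calculated via repeated measures analysis of variance".

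The Subjects section says that "written informed consent will be obtained and subjects will be randomized consecutively", so the baseline means have equal expectation in the two arms.

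**The concern.** Baseline is measured before any treatment, so it carries no treatment effect. Making it an outcome level lets the model estimate a group difference at baseline that is zero in expectation by design. The chance part of that difference then enters every contrast with baseline at full weight. If the score at a later visit rises by less than one point per point of baseline, full weight over-corrects and adds noise.

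At stake is precision, and possibly power, for the primary comparison and for the EORTC scales analysed in the same way. The baseline is already collected, so any precision lost is lost without need.

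**Working it through.** **Inputs.** From the protocol: four assessments with baseline first, two randomised groups, the interaction as primary test, two-sided alpha 0.05. The protocol states no sample size, SD, correlation or effect shape, so there is no figure of its own to reproduce. Everything below is assumed for illustration: equal arms, SD s = 2, n = 20 or 40 per arm, no dropout.

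**Single visit.** Let β be the slope of follow-up on baseline. The change score has variance (residual variance given baseline) + (1 − β)² × (baseline variance); the adjusted score has the first term only. The two agree when β = 1.

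With equal variances β = ρ:

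- change: 2(1 − ρ)s²
- adjusted: (1 − ρ²)s²
- ratio: (1 + ρ)/2, which is 0.70 at ρ = 0.4, 0.75 at 0.5, 0.85 at 0.7 and 0.95 at 0.9

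Estimating the slope multiplies the ratio by 1 + 1/(2n − 4). At 20 per arm it becomes 0.719 at ρ = 0.4 and 0.976 at ρ = 0.9, so the variance is 28% to 2% lower.

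The equal-variance condition matters. With baseline SD 1.4, follow-up SD 2 and ρ = 0.7, β = 0.7 × 2/1.4 = 1.0. The ratio is then 1.00, or 1.03 at 20 per arm: no gain. The entry rule of NRS 3 or more may itself narrow the baseline. For a normal score with mean 4 or 5 and SD 2 cut at 3, the baseline variance V is 1.945 or 2.519. The ratio 4(1 − ρ²)/[4(1 − ρ²) + (1 − ρ)²V] is then 0.83 or 0.79 at ρ = 0.4, and 0.92 or 0.90 at ρ = 0.7. The saving is smaller but remains.

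**Joint 3-df test under compound symmetry.** Take group differences d = (0, 0.5, 1, 1) at the four times (effect sustained to follow-up), ρ = 0.5, n = 40.

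- Planned: λ = (n/2) × Σ(d − mean)²/[(1 − ρ)s²] = 20 × 0.6875/2 = 6.88
- Gain from adjustment, with e the three post-baseline differences: n(Σe)²/[8s²(1 + 3ρ)] = 40 × 6.25/80 = 3.125, so λ = 10.00

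By noncentral F the power is 57% planned and 73% adjusted; simulation gave 56% and 73%.

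**Other covariance patterns** (simulated power; adjusted = unstructured joint test given baseline; the last column of differences is in percentage points):

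| Correlation | Effect | n per arm | Planned, uncorrected | Adjusted | Difference |
|---|---|---|---|---|---|
| Compound symmetry 0.5 | sustained | 40 | 56% | 73% | +17 |
| Compound symmetry 0.5 | sustained | 20 | 32% | 40% | +8 |
| AR(1) 0.7 | sustained | 40 | 59% | 60% | +1 |
| AR(1) 0.7 | sustained | 20 | 32% | 28% | −4 |
| AR(1) 0.7 | end of treatment only | 40 | 71% | 88% | +17 |
| AR(1) 0.9 | sustained | 20 | 70% (63% with Greenhouse-Geisser) | 56% | −14 (−7) |

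For an end-of-treatment-only effect under compound symmetry 0.5, 40 per arm, calculated power is 62% either way. The AR(1) 0.7 gain for that shape comes mostly from modelling the covariance: an unadjusted multivariate test of the same changes reached 89%.

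**Type I error of the planned test.** 5.3% under compound symmetry; about 5.5% to 7% under AR(1) 0.7 to 0.9 without a sphericity correction.

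**The case against.** The strongest reply is that nothing here is wrong. The objective is to compare changes, and the interaction does that. Covariates and covariance structure are often left to the SAP, which is not at hand. The planned test can even be the more powerful one in small samples.

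Most of this stands and sets the severity. It does not remove the point, because the protocol itself fixes the primary model, with its four levels and its test. Nor does adjustment change the objective: with baseline as covariate, the group difference in change equals the group difference in follow-up score.

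Stronger conclusions that a reader might draw are not supported:

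- *That the planned test is biased or invalid.* Randomisation makes the baseline means equal in expectation, and regression to the mean after the entry threshold is expected equally in both arms. The only condition on the error rate is sphericity or a correction, and the SAP may provide one.
- *That a definite amount of power is being lost, large for a sustained effect and nil for an effect at end of treatment only.* That pattern belongs to compound symmetry; under AR(1) 0.7 it reverses.
- *That adjustment can never cost more than a few points.* At AR(1) 0.9 with 20 per arm, the unstructured test loses about 7 points even against the corrected planned test.

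**Conclusion.** The point holds as an efficiency improvement of low severity. The planned interaction matches the objective and is unbiased, with nominal type I error given sphericity or a correction. It gives up precision at each visit whenever the baseline slope is below 1: with equal variances, 30% down to 5% of the variance for correlations of 0.4 to 0.9, and slightly less once the slope is estimated.

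The algebra at a single visit is firm under those conditions. The power consequence for the joint test is not. It depends on sample size, correlation, covariance pattern and effect shape, none of which the protocol gives, and the simulated figures only show how wide the range is.

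**What to change.** In the Statistical analysis section, replace the primary model by one of the following:

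- the three post-baseline assessments as repeated outcome, with group, visit, group-by-visit, baseline score and baseline-by-visit, testing group jointly with group-by-visit; or
- a four-level longitudinal model that constrains the baseline mean to be common to both arms.

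In the first model, do not test group-by-visit alone: a sustained effect goes largely into the group term. In the sustained example (compound symmetry, 40 per arm) the interaction alone has about 15%, 19% and 30% power at ρ = 0.3, 0.5 and 0.7.

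Pre-specify the covariance approach with the expected sample size in mind, since a fully unstructured joint test can lose power in small samples. In the compound-symmetry simulations, an adjusted test with that same structure lost nothing beyond simulation error at ρ = 0.3 to 0.7; it was not tried under decaying correlation.

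Apply the same to the EORTC scales analysed by repeated measures ANOVA, each with its own baseline. If the SAP already adjusts for baseline, align the protocol text with it.

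The cost is wording only: the paresthesia score and the questionnaires are already collected at every assessment.
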